4.9.1 Early Termination Study Visit

Subjects who withdraw from the study will have all procedures enumerated for the early termination visit as per the study schedule and timeline (Appendices 1 and 2) either in person or by telephone visit.

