5.2.4 AGS Scale

Refer to Appendix 5 for AGS Scale, which will be applied at baseline, 3 months, 6 months, 9 months, 12 months and every subsequent study visit through neurologic exam and conversation with parents.

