6 STATISTICAL CONSIDERATIONS

6.1 Primary Endpoint

The primary endpoint will be the change in the AGS scale from baseline to 52 weeks.

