APPENDIX

Appendix 2. Study Timeline*

Procedures performed solely for research purposes are indicated in bold text

		Screening		Treatment						Early Termination	Safety Closeout
Visit number	Required	1	2		4 ^p		201 ^p	210º	212 ^p , 213°, 214 ^p , 215°, 216 ^p , 217°, 218 ^p , 219°, 220 ^p , 221°, 222 ^p , 223°, 224 ^p , 225°, 226 ^p , 227°, 228 ^p , 229°, 230 ^p ,231°	ET ^{ap}	801 ^q
	Optional ^q			3		5		205, 206,	212A, 213A, 214A, 215A, 216A, 217A, 218A, 219A, 220A, 221A, 222A, 223A, 224A, 225A, 226A, 227A, 228A, 229A, 230A		
Weeks from enrollment		4 to .5	0	2	4	8	12	16 to 52⁵	60 to 288°		292
Number of days at visit		28 to 2	Variable ^d	1-5	1-5	1-5	1-5	1-5	1-5	1-5	1-5
Visit window (days) ^e		2	+ 2	+ 2	+ 2	+ 2	+ 2	+ 5	+ 5	+ 5	+ 5
Informed consent	_	х									
Demographic characteristics	_	х									
Height	_	х	х	х	Х	Х	х	x	×	x	х
Weight	_	х	х	x	х	Х	х	х	x	x	x
Confirm tuberculosis test	_	X ^f									
Chest x-ray		Xa									
Electrocardiogra m (ECG)	_	Xr									
Echo cardiogram	_	Xr									
Review inclusion/		х									

exclusion											
criteria											
Medical history	-	Х									
Physical examination	_	х	Х	Х	Х	x	х	х	x	x	x
Vital signs	_	х	x	х	x	х	x	х	x	x	Х
Diary Scores	-	Xi	Х	Х	x	х	х	х	x	×	
Concomitant medications	_	х	Х	х	Х	x	х	х	Х	x	X
Previous Therapy		x									
AGS scale, GMFM-88 and functional neurologic testing, CLASI	_	X						Xs	Xs		
Adverse events	 		x	х	x	x	х	х	X	х	х
Dispense baricitinib ^k	_		x					x	x		
Laboratory											
Hematology	-	Xh	Xi	х	х	х	х	х	x	Xw	Xw
Serum chemistry ^v	_	X ^h	X ^j	х	Х	x	х	x	Х	Xw	Xw
Lipid panel		X ^h				x	х	х	x	Xw	
Urinalysis	-	X ^h	Xj	х	Х	х	х	х	x	Xw	Xw
IGF-1 [×]	-		х					x	x		
Vitamin D							Xw	Xw	Xw	Xw	Xw
HBsAg, HBcAb, HBsAb	 	X									
Hepatitis C antibody		XI									

HIV		XI									
		~									
HSV, EBV, CMV	-	XI	Xw								
Lymphocyte testing (T cell subset)		X ^h					x	x	x		
lgG	_	X ^h					x	х	X		
Cystatin C							Xw	Xw	Xw	Xw	Xw
Thyroid stimulating hormone and T4		Xf					Xw	Xw	Xw	Xw	Xw
Serum pregnancy test ^m		X ^h									
Urine pregnancy test ^m			х	Х	х	Х	х	х	x		
BK virus serum ^u		X ^h	Х	Х		Х	Х	х	x	Xw	Xw
Serum baricitinib concentration ⁿ			X	X	x	х	X	x	X	Xw	
IFN signaling score	_	X ^t	Х	Х	х	Х	Х	Х	x	Xw	Xw
Hand/wrist/finger s X-rays ^x			х					х	x		

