Abbreviations: ET = early termination; HBsAg = hepatitis B surface antigen; HBcAb = hepatitis B core antibody; HBsAb = hepatitis B surface antibody; HIV = human immunodeficiency virus; SAVI = STING-associated vasculopathy with onset during infancy.

- a. Early termination visit is required if early termination occurs.
- b. Visits occur at approximately 4-week intervals during Weeks 16 through 52 (including both required and optional visits).
- c. Visits occur at approximately 12-week intervals during Weeks 60 through 288.
- d. Visit 2 encompasses the initial dosing period and can vary in time depending on whether the patient progresses through the first and second dose escalation during this period. Four days is the minimum time.
- e. Every effort should be made to schedule patient visits within the allowable visit window; however, if a patient visit is scheduled outside the visit window, it will not be considered a protocol violation.
- f. If results are available from testing within 1 month, then the patient will not have to be retested.
- g. Chest X ray will be performed on a clinical basis and results reviewed during screening. If chest x-ray was not performed clinically within 6 months prior to the study, it will be performed as part of the research study.
- h. If results are available from testing within 1 month or as part of the pre-screening period, then the patient will not have to be retested at Visit 1.
- i. At least 2 weeks of diary scores are required prior to beginning investigational product.

- j. Collect prior to each dose escalation. Investigator will review to ensure dose escalation is appropriate. Collect prior to the last dose given at Visit 2.
- k. Drug will be dispensed at visit 2, visit 204, and then every 6 months during onsite visits. However, when traveling to the investigative site is not considered safe for the patients due to unforeseeable events (see footnote o), such as public or personal health emergencies, the study drug may be dispensed for a longer time.
- I. If results are available from testing within the previous 3 months, then the patient will not have to be retested.
- m. For female patients of child-bearing potential: a serum pregnancy test will be performed at Visit 1 and a urine pregnancy test (local laboratory) will be performed at Visit 2 to determine study eligibility. At subsequent visits, a urine pregnancy test will be performed.

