- n. Baricitinib concentration samples will be collected at on-site visits. Samples will be collected after beginning baricitinib therapy and at each dose escalation, and may be collected at each study visit for safety monitoring. However, when traveling to the investigative site is not considered safe for the patients due to unforeseeable events (see footnote o), such as public or personal health emergencies, baricitinib concentration samples will not be collected.
- o. These required visits should be performed at the investigative site. However, in some circumstances, unforeseeable events, such as public health emergencies, states of emergency related to civil unrest, or weather emergencies, or individual health emergencies (affecting the patient or a caregiver), may create situations where it is unsafe for patients and their families to travel to the study site for in person assessments. In that case, the visits will be conducted using video operations. The changes from an in person evaluation, including differences to the study outcome collection, will be reported as a minor protocol deviation to the IRB at the time of continuing review.
- p. These required visits may be performed at the investigative site or as a telephone visit. If a telephone visit is performed, lab samples should be obtained locally and the required labs to be reported are: total bilirubin, direct bilirubin, alanine aminotransferase (ALT), aspartate aminotransferase (AST), blood urea nitrogen (BUN), creatinine, and all hematology. In addition, physical examination is not needed if a telephone visit is performed.
- q. Optional visits may be performed at the investigative site or as a telephone visit but will not be considered a protocol violation if not performed. If a telephone visit is performed, lab samples should be obtained locally. Optional visits between weeks 60 to 288 would only be performed to allow patients to re-align with the initial in-person versus phone visit schedule, in cases where this schedule would be disrupted by an unforeseeable event (refer to footnote "o" for examples of such events) to enhance patients safety. For instance, if a patient were not able to come on-site for several months or years, an in-person visit may be necessary for the providers to assess the patient in-person.
- r. EKG and echocardiogram will be performed on a clinical basis and reviewed during screening.

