- s. Functional outcome assessments will be conducted at baseline and every six months.
- t. Three baseline IFN scores will be collected, each at least 5 days apart and not more than 60 days before start of study medication.
- u. Patients will be monitored for BK viremia at baseline, and every six months until they reach two years of age. Over two years of age, complete follow-up BK testing will be performed if any of the following is observed: blood in urine (as defined by 5-10 RBCS in HPF), protein in urine (positive), decrease in eGFR (30 <60 mL/min/1.73 m²). Follow- BK testing includes urine and serum BK testing. Abnormal urine results with urinary tract infection, in the absence of change in eGFR, do not necessitate BK testing.
- v. The creatinine should be measured using the IDMS (Isotopic Dilution Mass Spectrometry) technique to monitor the eGFR if available. Other methods are allowed but are not preferred. Laboratory testing using other methods will not be used to monitor the eGFR.
- w. These labs may be drawn (optional).
- x. For bone growth monitoring, IGF-1 will be completed yearly, and hand/wrist/fingers X-rays will be completed at baseline, 6 months, 12 months and then every 12 months (not after a bone age demonstrating complete growth).

* Visit schedule will be extended beyond Week 288 to long term follow up if transition to commercial supply is not possible for a patient. Visit will then be extended until patient transitions to commercial supply. The same tests and procedures that were completed during the study will be continued. Visit numbers will continue per the same numbering logic (232, 233, 234...).

Appendix 3. Dose Escalation Schedule for Patients with eGFR ≥60 mL/min/1.73 m2 or Normal eGFR for Age <24 Months (see footnote below^c)

If a change in the patient's weight during the study would place the patient in a different weight range, changes over time are permitted.

		Morning Dose	Noon Dose	Afternoon Dose	Evening Dose	Total Daily Dose	Dosing Frequency
FR ≥ 60 mL/min/1.73	m ²						
5-< 10 kg	Initial	1 mg	1 mg	0 mg	1 mg	3 mg	TID
	Escalation 1	1 mg	1 mg	1 mg	1 mg	4 mg	QID
10-< 20 kg	Initial	2 mg	2 mg	0 mg	2 mg	6 mg	TID
	Escalation 1	2 mg	2 mg	2 mg	2 mg	8 mg	QID
20-< 40 kg	Initial	3 mg	-	0 mg	3 mg	6 mg	BID
	Escalation 1	3 mg	—	2 mg	3 mg	8 mg	TID
≥ 40 kg	Initial	4 mg	_	-	4 mg	8 mg	BID
	Escalation 1	5 mg	—	_	5 mg	10 mg	BID
	Escalation 2	6 mg	_	_	6 mg	12 mg	BID

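### Section 5.2.4 and Appendix 2 give different schedules for the primary AGS scale, and Appendix 2 does not mark it at early termination, so some early leavers may have no on-treatment score

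*Combined protocol and SAP*

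**What the plan says.** - Section 6.1: "The primary endpoint will be the change in the AGS scale from baseline to 52 weeks".
- Section 5.2.4, on the AGS scale: "which will be applied at baseline, 3 months, 6 months, 9 months, 12 months and every subsequent study visit". The same section bases the score on a neurological examination together with the parents' account.
- Appendix 2, the row labelled "AGS scale, GMFM-88 and functional neurologic testing, CLASI": marked at Visit 1, in the weeks 16 to 52 column and in the weeks 60 to 288 column. It is blank at Visit 201 (week 12), at early termination and at Visit 801. The two later marks carry footnote s: "Functional outcome assessments will be conducted at baseline and every six months".
- Appendix 2, footnote a: "Early termination visit is required if early termination occurs".
- Section 4.9.1: "Subjects who withdraw from the study will have all procedures enumerated for the early termination visit as per the study schedule and timeline", with a reference to Appendices 1 and 2. The text of Appendix 1 is not in the supplied document.
- Appendix 2, footnote p, which covers Visit 201, early termination and alternate later visits, allows a telephone visit and adds that "physical examination is not needed if a telephone visit is performed".
- Section 6.4 expects that some patients will be lost or will die before one year, gives no rate, and says that GEE and QLS need the missing-at-random assumption.

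**The concern.** The two schedules cannot both be followed. Both are stated in complete sentences, so a broken table does not explain the difference. Footnote s cannot be confined to the GMFM-88, because its row names the AGS scale first.

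What is at stake is the information kept on patients who leave early. Early termination is a required last contact. Appendix 2 marks diary scores, adverse events and physical examination there, but not the scale on which the trial will be judged. A patient who dies or deteriorates in the first half-year could then leave no on-treatment score. The pre/post model would rest on patients who stayed, under a missing-at-random assumption that the data could do little to support. The longitudinal analyses in Section 6.3.3.1 also depend on how many interim scores exist, and the current text leaves that open.

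**Working it through.** **1. The plan's own power figure.** Section 6.4 gives 98.3% power for 30 pairs at effect size 0.77, with a two-sided paired t-test at 0.05. The noncentral t with 29 degrees of freedom and noncentrality 0.77 × √30 gives 98.27%, so the figure reproduces. With 25 pairs the power is 95.8%. At effect size 0.53 it is 80.1% with 30 pairs and 72.0% with 25. With about 45 evaluable patients expected, losing a few early leavers is not mainly a power problem.

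**2. Scores due in year 1.**

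| Schedule | Scores due (months) | Post-baseline | First on-treatment score |
|---|---|---|---|
| Section 5.2.4 | 0, 3, 6, 9, 12 | 4 | about week 13 |
| Appendix 2, footnote s | 0, 6, 12 | 2 | about week 26 |

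Both include baseline and month 12.

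**3. Patients with no on-treatment score.** The documents give no dropout rate. Assumption: constant hazard h = −ln(1 − d)/52 for 52-week dropout d. The expected number leaving before week w is N × (1 − e^(−hw)). The 18% row is about 10/55, from roughly 45 evaluable of 55.

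Upper bound, all N = 55 recruited directly:

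| d | Section 5.2.4 (w = 13) | Appendix 2 (w = 26) |
|---|---|---|
| 5% | 0.7 | 1.4 |
| 10% | 1.4 | 2.8 |
| 18% | 2.7 | 5.2 |
| 30% | 4.7 | 9.0 |

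Transferred patients bring their compassionate-use data (Section 6.3.3.6), and Section 6.4 reports preliminary AGS data on 35 patients. If those 35 are all among the 45 evaluable or 55 enrolled (assumption), direct recruits number 45 − 35 = 10 to 55 − 35 = 20. With d from 10% to 30%:

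- Appendix 2: 0.5 (10 recruits, 10%) to 3.3 (20 recruits, 30%).
- Section 5.2.4: 0.3 to 1.7.

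**4. Precision of one patient's slope.** With independent errors, the slope variance is σ²/Σ(t − t̄)².

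- Year 1: Σ = 0.625 for {0, 0.25, 0.5, 0.75, 1} and 0.5 for {0, 0.5, 1}. The ratio is 1.25.
- Full follow-up: Section 5.2.4 gives 5 scores to week 52 plus (288 − 60)/12 + 1 = 20 later ones, 25 in all. Six-monthly scoring at weeks 0, 26, …, 286 gives 12. The sums are 185,066 and 96,668 weeks², a ratio of 1.91.

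Under a pure Markov correlation (assumed six-month correlation 0.90 to 0.98, no extra visit noise), the generalised least squares ratios are about 1.00 in year 1 and 1.01 over full follow-up.

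**The case against.** The strongest reply is that the primary contrast is untouched. Baseline and week 52 are due under either schedule, and a patient who leaves before week 52 lacks that score whichever schedule is right. This stands. An early-termination score would not replace the week-52 value; it would add an on-treatment observation to the GEE.

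A reader might infer that early leavers drop out of the primary analysis altogether. The documents do not support that. The main model in Section 6.3.2 uses time before and after treatment start, so a patient with only pre-treatment scores still informs the pre-treatment part. Such a patient is lost from the paired comparisons and adds nothing on treatment.

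A reader might also take the 25% and 90% variance increases as the size of the problem. They hold only for independent errors and describe one patient's slope. Section 6.3.3.1 itself calls a Markov structure plausible, and under strong Markov correlation the difference nearly vanishes.

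Three further points soften the concern:

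- Appendix 1 is not in the supplied text and may list the scale at early termination. If so, it and Appendix 2 would still need to agree.
- Sections 1.5 and 6.3.3.2 say the scale can be scored from clinical notes, so some missing scores might be recovered. No rule provides for this in treated patients, and footnote p drops the physical examination at telephone visits.
- Section 4.1 moves on-site visits to video in emergencies, and Section 6.4 commits to reviewing reasons for dropout. Neither says how the AGS scale is scored remotely. Section 5.2.5 does give such a procedure for the GMFM-88.

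**Conclusion.** The point holds as a scheduling conflict on the primary scale, with a gap at early termination in Appendix 2. It affects interim scores and early leavers, not the collection of baseline and week 52 in patients who stay.

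The number affected is probably small: from under one to about three patients under the six-monthly schedule if 10 to 20 are direct recruits and one-year dropout is 10% to 30%. The ceiling is about 9, if all 55 were direct recruits and 30% left. These counts rest on an assumed constant dropout hazard and an assumed share of direct recruits. The gain in slope precision from the denser schedule runs from negligible to 25% in year 1 and about 90% over full follow-up, depending on the error correlation.

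The harm is possible bias and inconsistent collection. Loss through death or decline may be informative, but the documents do not show that it will be. The early-termination part is conditional on what Appendix 1 says.

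**What to change.** 1. Choose one AGS schedule that includes week 52 and state it identically in Section 5.2.4 and Appendix 2. If it differs from that of the GMFM-88 and CLASI, give the AGS scale its own row.
2. Mark the AGS scale in the early-termination column of Appendix 2, and in Appendix 1 if it is absent there.
3. State how the scale is scored at telephone and video visits, and record the mode of each assessment.

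The cost is protocol wording and one short scale at a visit that already takes place. Remote scores may be less exact than in-person ones, which is why the mode should be recorded.

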8.8 Safety Management and Monitoring Guidance

The following Appendices should be followed. Appendices 9-12 in particular serve as guidance for management of abnormal laboratory values identified during screening or safety follow-up of enrolled individuals.

Study schedule, Overall	Appendix 1
Study Timeline	Appendix 2
Dose Escalation Schedule for Patients with eGFR ≥60 mL/min/1.73 m2 or Normal eGFR for Age <24 Months	Appendix 3
Dose Escalation Schedule for Patients with eGFR 30 - <60 mL/min/1.73 m2 or for Age <24 Months with abnormal eGFR	Appendix 4
AGS severity scale	Appendix 5
Patient Daily Diary for AGS infants 0-6 months	Appendix 6
Patient Daily Diary for AGS > 6 months	Appendix 7
Clinical Laboratory Tests	Appendix 8
Management of Liver Enzyme Laboratory Values	Appendix 9
Management of Leukocyte associated laboratory testing and IgG	Appendix 10
Management of Anemia	Appendix 11
Management of Thrombocytopenia and Thrombocytosis	Appendix 12
Cutaneous LE Disease Area and Severity Index (CLASI)	Appendix 13
Dose tapering guidance	Appendix 14
Decision tree in case of infection suspicion or confirmation	Appendix 15
Concomitant medication approach in patients with AGS receiving baricitinib	Appendix 16

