9.4.2.1.1 Serious Infections and Viral Reactivation

Serious and sometimes fatal infections due to bacterial, mycobacterial, invasive fungal, viral, or other opportunistic pathogens have been reported in rheumatoid arthritis patients receiving baricitinib. The most common serious infections reported with baricitinib included pneumonia, herpes zoster, and urinary tract infection (see Adverse Reactions).

Among opportunistic infections, tuberculosis, multidermatomal herpes zoster, esophageal candidiasis, pneumocystosis, acute histoplasmosis, cryptococcosis, cytomegalovirus, and BK virus were reported with baricitinib. Some patients have presented with disseminated rather than localized disease and were often taking concomitant immunosuppressants such as methotrexate or corticosteroids.

As of March 2020, fungal pneumonia was reported in a single AGS patient receiving baricitinib and also receiving concomitant therapy with corticosteroids during the Lilly expanded access program. Vigilance for infections should remain high in particular in children with any concomitant medications increasing immunosuppression, or hematologic parameters suggestive of immunosuppression.

Prophylaxis for serious infections will be recommended based on CD4, IgG, ANC and ALC levels as per section 4.6.

To minimize these risks, screening includes careful assessment of infections prior to drug initiation, including HIV, hepatitis, tuberculosis, HSV, CMV, EBV, and BK virus. In addition, ongoing evaluations, including clinical assessments for infection, and laboratory testing for HSV (IgG/IgM), CMV PCR, EBV PCR and tuberculosis (via quantiferon gold testing, only for patient in endemic regions) during treatment, will be conducted as clinically indicated.

Patients will be monitored for BK viremia at baseline, and every six months until they reach two years of age. Over two years of age, complete follow-up BK testing will be performed if any of the following is observed: blood in urine not explained by a urinary

tract infection (as defined by greater than 10 RBCS in HPF), equal to or greater than 1+ protein on a first morning urine sample not explained by a urinary tract infection (positive), decrease in eGFR ($30 - 60 \text{ mL/min}/1.73 \text{ m}^2$).

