9.8.8 Protocol Violations

Protocol violations or deviations are any non-adherences to the procedures outlined in this document and include, but are not limited to, late evidence of exclusion criteria,

missed evaluations, incorrect timing of evaluations or dosing, and intake of inadmissible medication. After a subject has been enrolled, it is the investigator's responsibility to make any reasonable effort to avoid and, if necessary, correct protocol deviations. Major protocol violations will be reported to the DSMB at the time of a meeting, the IRB and the FDA. All protocol violations will be listed and the admissibility of the subjects' data will be discussed with the Medical Monitor prior to the statistical analysis. In case any emergency or AE occurs that requires a protocol deviation in the particular case, the investigator should contact the Medical Monitor and DSMB as soon as possible to enable a decision on whether the subject's participation in the study may be continued.

[figure not shown]

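### For patients over two, the haematuria trigger for follow-up BK virus testing is more than 10 RBC/HPF in Section 9.4.2.1.1 but 5-10 RBC/HPF in Appendix 2, footnote u

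*Combined protocol and SAP*

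**What the plan says.** Section 9.4.2.1.1 of the combined protocol and SAP deals with serious infections and viral reactivation. It lists BK virus among the opportunistic infections reported with baricitinib. BK viremia is monitored at baseline and six-monthly until age two. After that age, full follow-up BK testing depends on any one of three findings:

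- blood in the urine that a urinary infection does not explain, "as defined by greater than 10 RBCS in HPF";
- protein, given as "equal to or greater than 1+ protein on a first morning urine sample not explained by a urinary tract infection (positive";
- a decrease in eGFR into the 30-60 range.

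Footnote u of Appendix 2 repeats the rule for the same patients with the same lead-in. Its first trigger is "blood in urine (as defined by 5-10 RBCS in HPF". Its second is protein described only as positive, with no grade and no sample type. Its third is the same eGFR range. It adds that "BK testing includes urine and serum BK testing", and it covers infection separately: "Abnormal urine results with urinary tract infection, in the absence of change in eGFR, do not necessitate BK testing".

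The schedule row labelled "BK virus serum" carries footnote u. Section 8.8 introduces a list that includes Appendix 2 with "The following Appendices should be followed". Section 9.8.8 states: "Protocol violations or deviations are any non-adherences to the procedures outlined in this document".

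**The concern.** The population, the test and the triggering finding are the same, but the cut-off differs. Once scheduled monitoring ends at age two, these findings decide whether a BK test is required. In a child with neither of the other two triggers, the red-cell count decides it alone.

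Take a child over two with 7 RBC/HPF at a post-baseline visit, no urinary infection, no positive urine protein and no eGFR decrease. Footnote u requires urine and serum BK testing; Section 9.4.2.1.1 does not. Staff working from Section 9.4.2.1.1 would omit a test for a recognised risk of the drug. Because Section 9.8.8 defines deviations so broadly, that omission would comply with one part of the protocol and deviate from another.

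**Working it through.** The plan gives no figure to reproduce, so the check sets the two texts side by side.

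**Inputs.** Section 9.4.2.1.1: more than 10 RBC/HPF. Appendix 2, footnote u: 5-10 RBC/HPF. Held fixed: age over two, post-baseline, no urinary infection, urine protein negative on any sample, no eGFR decrease. Only the red-cell trigger can then act.

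**Is a BK test triggered?**

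| RBC/HPF | Section 9.4.2.1.1 | Footnote u as a floor of 5 | Footnote u read literally |
|---|---|---|---|
| 4 | no | no | no |
| 5 | no | yes | yes |
| 7 | no | yes | yes |
| 10 | no | yes | yes |
| 11 | yes | yes | not named |
| 15 | yes | yes | not named |

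**Floor reading.** The texts disagree from 5 to 10. If laboratories report whole numbers, that is 10 − 5 + 1 = 6 values. They agree below 5 and above 10.

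**Literal reading.** The two ranges do not overlap. Every result of 5 or more is then treated differently: 5 to 10 is named only in the footnote, and above 10 only in Section 9.4.2.1.1.

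**Do the other terms explain the difference?** No. Both texts exempt abnormal urine attributable to a urinary infection, in substance, and both use the same eGFR range. Neither is an amendment log or a summary of changes.

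**When can it arise?** Appendix 2 marks urinalysis in 8 columns: Visit 1 and Weeks 0, 2, 4, 8, 12, 16-52 and 60-288. BK is already assessed at baseline whatever the urine shows, so Visit 1 and Week 0 add little, at most the urine part of the test. That leaves 8 − 2 = 6 post-baseline columns. Two of these (Weeks 2 and 8) are optional visits. Urinalysis is also optional at early termination and Week 292. Two features limit it further. The laboratory tests required at a telephone visit (Appendix 2, footnote p) do not include urinalysis, and sediment is examined under the microscope only after an abnormal routine urinalysis (Appendix 8, footnote f).

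**Effect of each possible floor, against footnote u read as a floor of 5.** At least 5 in both places adds tests under Section 9.4.2.1.1 at the 6 values and changes nothing under footnote u. More than 10 in both places changes nothing under Section 9.4.2.1.1 and removes the tests that footnote u now requires at the 6 values.

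**The case against.** The strongest reply is that the protocol points staff to a working text. The BK row carries footnote u, Section 8.8 directs staff to the appendices, and Section 9.4.2.1.1 sits within the risk assessment. Someone ordering tests from the schedule would reach the footnote, and testing from 5 upwards satisfies both texts. Other safeguards remain: the protein and eGFR triggers act independently, and Section 5.2.12.1 allows additional blood samples for safety. All of this stands, and it makes the matter minor. It does not remove the conflict, because Section 9.4.2.1.1 is operative text with its own number and no rule of precedence withdraws it.

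A reader might infer more than the documents support in four respects.

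- *That the conflict matters at every urinalysis from screening onwards.* Baseline BK assessment is unconditional, so the consequence is essentially post-baseline.
- *That six affected values measure the impact.* They only enumerate a range, on the floor reading and with whole-number reporting. Urinalysis is run by local laboratories, and the documents do not say whether they report counts or bands.
- *That the protein wording is plainly a second conflict, or plainly just an abbreviation.* The shared tag of positive suggests an abbreviation. But a positive result on a sample not taken first thing in the morning could count under footnote u and not under Section 9.4.2.1.1. The text leaves this open.
- *That 5 is the clinically correct threshold.* Nothing in the documents supports either value over the other, and Section 9.4.2.1.1 is the more fully specified text.

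**Conclusion.** The inconsistency is real: one mandatory safety test has two haematuria thresholds, with no statement of which governs. On the sensible reading of footnote u as a floor of 5, the practical risk runs one way. A site following Section 9.4.2.1.1 omits a test that the footnote requires at 5 to 10 RBC/HPF. That conclusion assumes a post-baseline result in a patient over two with no urinary infection and neither of the other triggers. On the literal reading the footnote also fails to name results above 10. Section 9.4.2.1.1 still requires testing there, so the documents do not support inferring that heavier haematuria is meant to go untested.

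The number of patients affected cannot be estimated from the documents. This is a minor internal inconsistency in safety monitoring, with no bearing on the efficacy analysis or power. It is still worth correcting, because it concerns a required test for a named drug risk.

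**What to change.** State one open-ended floor in both Section 9.4.2.1.1 and Appendix 2, footnote u. The conservative default is at least 5 RBC/HPF that a urinary infection does not explain, since it covers every result that either text would test. If the sponsor confirms that more than 10 is intended, state that in both places instead.

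In the same edit, have footnote u repeat or cross-refer to the protein criterion in Section 9.4.2.1.1 (1+ or more on a first morning sample), which settles whether the two are the same. The eGFR trigger and the urinary-infection exemption can stay as they are.

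The cost is a wording amendment in two places. A floor of 5 adds an unquantified number of urine and serum BK tests relative to Section 9.4.2.1.1. A threshold of more than 10 adds none relative to that section, but gives up the tests that footnote u now requires at 5 to 10.
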